4.3.4 Respiratory rate

Respiratory rate should be assessed after the patient has been quietly at rest for at least 5 minutes. Respiratory rate should be assessed by counting the number of breaths for a full minute by direct observation or palpation of the patient's chest wall. If a measurement of minute ventilation with Hans Rudolph Pneumotach system is scheduled, the respiratory rate may be taken as part of this test for a period of one minute. A numeric value of the number of breaths per minute as well as the quality of the breaths (i.e., normal, shallow, labored) should be recorded on the pCRF for each time point observed. Quality of breaths will not be measured during the cycle exercise test.

4.3.5 Minute ventilation

The total volume of gas that enters or leaves the lungs each minute is referred to as the minute ventilation. It is the product of tidal volume and respiratory rate. Tidal volume (V_T), and breathing frequency (*f*) will be determined with Hans Rudolph Pneumotach Research System. Calibrations will be completed before each test period.

 V_T (mL/min) and f (b/min) will be recorded on the pCRF for each time point measured.

4.3.6 Spirometry

Patients will be given the opportunity to attempt spirometry at screening visit to ensure that they can adequately perform the testing during study assessments.

Spirometry will be measured in the seated position. A minimum of three maneuvers will be completed at each timepoint. Two(2) of the measurements must be closely correlated (within 10%). The highest values for forced vital capacity (FVC), forced expiratory volume in one second (FEV₁) and peak expiratory flow (PEF) selected from the two measurements will be recorded on the pCRF. Patients should be allowed time to recover before starting the next test in the series of three; however, the time between tests should not exceed 3 minutes. Predicted values for spirometry were taken from Crapo³.

FVC, FEV₁, FEV₁/FVC ratio and PEF should be recorded on the pCRF.

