This will be a double-blind, randomized, 2 cohort, placebo-controlled, 2-period crossover, pharmacokinetic/pharmacodynamic study. Mild asthma and mild to moderate COPD patients are included so that qualification of the differences in physiologic response and subjective experience of dyspnea can be extrapolated to the expected treatment population. The age range encompasses that of the Phase II study where dyspnea was first observed.

The primary variable will be respiratory rate and minute ventilation, based on the hypothesis of affecting adenosine receptors and preclinical observations. Cardiopulmonary cycle exercise testing is included because provocation of the system may elicit measurable changes in physiological parameters that are not otherwise observed. A sub-maximal protocol will be used for the exercise testing, and patients may terminate the test prior to experiencing dyspnea if they experience symptoms, which limit further exercising. Exercise testing also provides an opportunity to simulate the conditions and study the respiratory responses that could contribute to the sensation of dyspnea during daily activities.

A loading dose of 450 mg is chosen to maximize the potential of eliciting dyspnea. This dose will establish safety margins for a clinical loading dose that may be up to 270 mg. Dosing to 3 days will allow for attainment of steady-state plasma concentrations. Again, this will provide for assessment of dyspnea under clinically relevant conditions. A placebo crossover will be performed because dyspnea is a highly subjective sensation, and therefore comparison to a placebo baseline is desirable. In a healthy elderly volunteer study presently completing in the clinic this dose was well tolerated with no reports of dyspnea to date. This study will conclude the clinical phase prior to the start of the respiratory study in mid asthma and mild to moderate COPD patients.

Genetic polymorphisms may affect patients' responses to drugs. Genetic analysis on genes that may be involved in development of dyspnea associated with AZD6140 treatment will improve the understanding of the potential mechanism of this effect of AZD6140. Due to the limited number of patients in this study and low incidence of dyspnea associated with AZD6140 treatment, all patients participating in the study will be required to donate blood for genetic analysis.

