3.3.2 Inclusion criteria

For inclusion in the study patients must fulfill all of the following criteria:

- 1. Give written informed consent and agree to comply with all requirements of the study (this includes giving consent to donate blood for genetic testing);
- 2. Generally healthy male or female, who have mild asthma or mild to moderate COPD according to the following criteria:

Cohort	Volunteer Type	Age Range	Respiratory criteria
Α	Mild Asthmatic	35 –75 years (inclusive)	Clinical diagnosis > 1 year; $FEV_1 \ge 70\%$ predicted; no exacerbation in past 8 weeks; reversibility demonstrated within the past year (\ge 12% or 200 mL)
В	Mild to Moderate COPD	55 – 75 years (inclusive)	Clinical diagnosis > 1 year; $FEV_1 \ge 50\%$ predicted; no exacerbation in past 8 weeks; FEV_1/FVC ratio < 75%; history of tobacco smoking > 10 pack year

- 3. Females must be of non-childbearing potential defined as surgically sterile (hysterectomized, tubal ligation, or bilateral oopherectomy)or post-menopausal (cessation of regular menses for 12 months);
- 4. Weight at least 50 kg and have a BMI between 18 to 32 kg/m² inclusive. (BMI will be calculated as weight in kg/height in m² and will not be reported on the case report form.);
- 5. Have normal physical examination, laboratory values and vital signs; stable chronic medical conditions unless the investigator considers an abnormality to not be clinically significant or a symptom of mild asthma or mild to moderate COPD;
- 6. Patients are able to communicate with the investigator, and to understand and comply with all study requirements.

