3.3.5 Discontinuation of patients from treatment or assessment

3.3.5.1 Criteria for discontinuation

Patients may be discontinued from study treatment and assessments at any time. Specific reasons for discontinuing a patient from this study are:

- Voluntary discontinuation by the patient, who are at any time free to discontinue their participation in the study without prejudice to further treatment
- Safety reasons as judged by the investigator and/or AstraZeneca including moderate to severe dyspnea that does not resolve or return to patient's baseline within 2 weeks.
- Severe non-compliance to protocol as judged by the investigator and/or AstraZeneca.

- Incorrect enrollment (ie, the patient does not meet the required inclusion/exclusion criteria) or randomization (ie, the patient is not allocated study drug as described in the protocol) of the patient.
- Patient lost to follow-up
- A suspected/manifested infection according to WHO risk categories 2, 3, and 4 (Refer to Appendix D).
- Non-exercising respiratory rate >25 per minute, heart rate >120 per minute or SaO_2 <85%; or FEV1 < 1 Liter; or Peak Expiratory flow < 80L/min; or negative change in Modified Borg Scale /Bidirectional Dyspnea scale >3 points on 2 successive assessments (exclude exercising). All these criteria should be at investigator's judgment in conjunction with clinical findings.

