6.4.3 Methods of statistical analyses

Statistical analysis will be carried out by Biostatistics at AstraZeneca, Wilmington, Delaware using SAS (version 8.2). Graphics to be included in the text or intended for use as supplemental figures and individual profile figures will be made using SAS or other software. Pharmacokinetic analysis will be carried out by, or under the guidance of, the Pharmacokinetic Section, Experimental Medicine, at AstraZeneca, Wilmington, Delaware.

No formal statistical analysis of the pharmacodynamic, pharmacokinetic or safety data will be done.

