6.4.4 Determination of sample size

The sample size for each cohort was chosen based on feasibility concerns, and the need to provide adequate information to support further development. The sample size was not based on any power calculations.

- 6.5 Interim analyses (not applicable)
- 6.6 Data presentation (not applicable)

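### Section 4.3.6 takes spirometry values only from the two maneuvers that agree within 10%, so a best effort more than 10% above an agreeing lower pair is not recorded

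*Combined protocol and SAP*

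**What the plan says.** Section 4.3.6 gives the whole rule. "A minimum of three maneuvers will be completed at each timepoint". Agreement is then required between two of them: "Two(2) of the measurements must be closely correlated (within 10" (the figure is a percentage). The highest FVC, FEV1 and PEF "selected from the two measurements will be recorded on the pCRF". So the values eligible for recording are those of the agreeing pair, not those of all acceptable maneuvers.

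The section does not say:

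- which of FVC, FEV1 or PEF the 10% applies to;
- whether it is 10% of the larger or the smaller value;
- which pair counts when more than one pair agrees;
- what happens when no two agree.

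Table 2 schedules spirometry 11 times per period from the Day 1 predose session onward: three on Day 1, two each on Days 2 and 3, three on Day 4 and one on Day 5. It is also done after the exercise test (Section 4.3.7.3) and at each spontaneous dyspnea episode (Table 3). Section 6.1.2 calculates changes from baseline within each period.

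Spirometry is not primary: "The primary variable will be respiratory rate and minute ventilation" (Section 3.2). Section 6.4.3 adds: "No formal statistical analysis of the pharmacodynamic, pharmacokinetic or safety data will be done".

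**The concern.** FEV1, FVC and PEF measure maximal effort. The highest acceptable blow is the best estimate of what the patient can do, and a low blow is more often a weak effort than a true value. A rule that first looks for any agreeing pair and then takes the maximum within it can select in the wrong direction. Two weak efforts that match each other satisfy it, and the one good effort is set aside. The session has then passed, so no further blow is called for.

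At stake is the quality of individual recorded values. Section 3.2 notes that earlier patients with dyspnea who were evaluated showed no bronchospasm, so FEV1 in this study will be read for the same purpose. A spuriously low post-dose FEV1 looks like a fall in airway function. A spuriously low predose value raises every later change from baseline in that period and can hide a fall. Only 8 to 12 patients per cohort are expected, summarized descriptively by time point, so single values carry some weight. The undefined terms also let two technicians record different numbers from the same blows.

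**Working it through.** The plan states no spirometry effect size, standard deviation or power. Section 6.4.4 says "The sample size was not based on any power calculations". There is therefore no figure of its own to reproduce.

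**Inputs from Section 4.3.6:** at least three maneuvers, two within 10%, highest value taken from those two. **Assumed, not in the documents:** within-session CV of 3%, 5% or 8%, and the shape of the error.

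**1. Minimum loss when the best is dropped.** Order the three values as low, middle and best (B). The best is excluded when it differs from the middle by more than 10% while low and middle agree. The recorded value is the middle one.

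- 10% of the larger value: loss > 0.10 × B.
- 10% of the smaller value: loss > B × (1 − 1/1.10) = 0.091 × B.

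The guaranteed loss reaches 200 mL at B = 0.200/0.10 = 2.0 L or B = 0.200/0.091 = 2.2 L. At B = 1.5 L it is only 150 mL or 136 mL.

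**2. Worked cases (FEV1, L).**

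| Blows | Low vs middle, % of larger | Middle vs best, % of larger | Recorded | Loss |
|---|---|---|---|---|
| 1.50, 1.62, 1.85 | 0.12/1.62 = 7.4% | 0.23/1.85 = 12.4% | 1.62 | 230 mL |
| 2.00, 2.10, 2.40 | 0.10/2.10 = 4.8% | 0.30/2.40 = 12.5% | 2.10 | 300 mL |
| 1.30, 1.35, 1.52 | 0.05/1.35 = 3.7% | 0.17/1.52 = 11.2% | 1.35 | 170 mL |

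The smaller-value denominator gives the same outcome in all three.

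A fourth set shows the ambiguity. With 2.00, 2.10 and 2.30, both 2.00/2.10 (4.8%) and 2.10/2.30 (0.20/2.30 = 8.7%) agree. The rule does not choose between them, so either 2.10 or 2.30 L could be recorded.

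**3. How often.** Three independent maneuvers per session were simulated. The symmetric model uses normal error. The skewed model uses a patient ceiling minus an exponential shortfall whose SD, as a fraction of the ceiling, equals the stated CV. Chance per session that the best is dropped (10% of larger value):

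| Assumed CV | Symmetric | Downward-skewed |
|---|---|---|
| 3% | 0.2% | 0.1% |
| 5% | 4.9% | 1.6% |
| 8% | 16.9% | 5.7% |

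With 10% of the smaller value, the symmetric figures are 0.4%, 7.2% and 19.4%. If the skewed model's SD is scaled to the mean rather than the ceiling, its figures are 0.1%, 1.3% and 4.9%.

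**4. Average effect.** In the symmetric model (larger denominator), mean understatement over all sessions is about 0.02%, 0.6% and 2.6% of the patient's mean level at CV 3%, 5% and 8%. One error of 230 mL in one patient moves a time-point mean by 230/8 = 29 mL with 8 patients, or 230/12 = 19 mL with 12.

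**The case against.** The best case for leaving the rule alone is that its practical effect is small. The same rule applies at every time point in both periods under double blinding, so it should not favor either treatment unless the drug changes blow-to-blow variability. Spirometry is secondary and no formal test depends on it. If poor efforts explain most of the spread, isolated high blows are uncommon and the lower frequencies apply. A minimum of three maneuvers already permits more. All of this stands and limits the size of the point. It does not change what the text tells the site to record.

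Several stronger readings are tempting, and the documents do not support them:

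- **That the loss exceeds a meaningful change set by the protocol.** None is set. The figure of 12% or 200 mL in Section 3.3.2 belongs to "reversibility demonstrated within the past year", an entry criterion for the asthma cohort only. In this review 200 mL is a yardstick of size, and the third worked case reaches neither 12% nor 200 mL.
- **That a PEF threshold is crossed.** No PEF change threshold exists. The recording rule affects PEF too, but there is nothing to measure the loss against.
- **That most patients will have an affected session.** Compounding over 11 sessions, 1 − (1 − p)^11 gives 2%, 43% and 87% for the symmetric model. Those figures stack an undocumented CV, symmetric error and independence between sessions, and the spread mostly reflects the assumptions.
- **That the rule would force discontinuations.** Blows of 0.93, 0.98 and 1.10 L would be recorded as 0.98 L, on the other side of one limit in Section 3.3.5.1 ("FEV1 < 1 Liter; or Peak Expiratory flow < 80L/min"). That section leaves all such criteria to the investigator's judgment alongside clinical findings, and the investigator can consider the 1.10 L blow. This is a point about measurement only.

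**Conclusion.** The point holds as a defect in the recording rule. Read literally, Section 4.3.6 excludes a best maneuver that stands more than 10% above an agreeing lower pair, and nothing elsewhere in the documents corrects this. When it happens, FEV1 is understated by more than 9.1% or 10% of the best value, according to the denominator. That means at least 200 mL once the best FEV1 is about 2.0 to 2.2 L.

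The size of a single error follows from the text alone. The frequency does not. It rests on an assumed CV of 3% to 8% and an assumed error shape, and runs from about 0.1% to 17% of sessions (10% of the larger value). At 3% the problem is rare under either shape.

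The expected consequence is extra noise in single time-point values and changes from baseline of a secondary, descriptively summarized variable. A reader might infer bias between AZD6140 and placebo, but the common rule and the blinding give no reason to expect it. The correction is worth making because it costs almost nothing and also settles the undefined terms.

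**What to change.** Amend Section 4.3.6 to say:

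- The highest FEV1, the highest FVC and the highest PEF from all acceptable maneuvers at the time point are recorded, whether or not they come from the same blow.
- The existing 10% agreement check applies to the two highest values. State which variable or variables it covers and whether the 10% is of the larger or the smaller value.
- If the check is not met, the highest values are still recorded and the session is flagged on the pCRF.

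With this change 1.50, 1.62 and 1.85 L would be recorded as 1.85 L with a flag, and the loss from the selection rule becomes zero. In 2.00, 2.10 and 2.30 L the choice of pair no longer matters.

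The cost is a few lines of protocol text, one flag field, and an occasional extra blow or flagged session. The sessions affected are those in which the best is dropped now, plus those with no agreeing pair, which the present text leaves unresolved.

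A tighter tolerance or a fixed maximum number of blows is not needed. In the symmetric model the two highest FEV1 values differ by more than 5% in 11%, 32% and 52% of sessions at CV 3%, 5% and 8%. A 5% limit would therefore prompt many repeats at time points that also carry timed PK samples.

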4.3.7 Cycle exercise testing

Tidal volume (V_T) and oxygen saturation (SpO_2) by pulse oximetry will be monitored throughout exercise testing and during exercise recovery.

On Study Day 4 of Periods I and II, an incremental cycle exercise test will be performed to a symptom-limited maximum. Refer to Table 2 for specific time.

4.3.7.1 Testing equipment

Exercise testing will be conducted using a cardiopulmonary exercise testing system and an electronically braked cycle ergometer, with a constant pedaling frequency of 50-70 revolutions per minute (rpm). Minute ventilation, tidal volume and respiratory rate will be monitored during the cycle exercise testing using Hans Rudolph Pneumotach system. Oxygen saturation by pulse oximetry and electrocardiographic monitoring will also be carried out continuously throughout testing.

The cycle ergometer should have a range of at least 0-600W with an accuracy of 2% or 3W above 25W.

4.3.7.2 Patient preparation

Patients should not eat for at least 2 hours before any exercise challenge. Patients should dress appropriately for the exercise challenge. On arrival in the laboratory, a detailed explanation of the testing procedure and equipment should be given to the patient, outlining the risks and potential complications.

Before exercise, ECG electrodes will be carefully placed and secured after preparing the skin to ensure good recordings (if necessary, the area of the electrode placement should be shaved). Just prior to exercise, the patient will be informed that he/she must signal any unexpected difficulty, ie, the patient is advised to point to the site of discomfort if chest or leg pain is experienced. A signal, such as a wave, should also be used when the patient wishes to terminate the test. Good communication with the patient throughout the whole procedure will increase the patient's confidence and helps to ensure a good effort.

Seat height should be adjusted so that the patient's legs are almost completely extended when the pedals are at the lowest point and the cycling rhythm practiced. When the patient is seated comfortably at the desired seat height, the distance between the seat and the floor will be measured and recorded. The same seat height will be used in Periods I and II for the patient.

4.3.7.3 Symptom-limited incremental cycle exercise test

Before exercise, while seated comfortably on the cycle ergometer, the patient will be fitted with the Hans Rudolph mask and will breathe for 3 minutes. V_T will be measured throughout the exercise test. Oxygen saturation by pulse oximetry and electrocardiographic monitoring of heart rate (HR) will be carried out throughout the testing. All variables will be recorded as 30 second averages at each workload and values at end-exercise (last 30 seconds of exercise).

The initial work rate will be set at 0 watts (i.e., loadless pedaling). The patient will perform 2 minute of loadless pedaling prior to increasing the work rate. The patient will begin to pedal at 50-70 rpm and will be encouraged to maintain this pedaling frequency throughout the exercise challenge. The patient is encouraged to continue exercise for as long as possible (i.e., to symptoms that limit exercise or maximal exercise).

At the end of each 2 minute interval, the work rate will be increased in increments of 25 watts.

The patient will exercise until:

- Until 80% of maximum predicted heart rate achieved; OR
- Limited by symptoms (i.e., is unwilling to continue exercising because of discomfort associated with the exercise); OR
- Unable to maintain a pedaling frequency of at least 40 rpm despite continued encouragement to increase the frequency to 50-70 rpm; OR
- Unable to continue safely (in the opinion of the supervising technician); OR

At the end of the exercise, the time of exercise is recorded (minutes and seconds): time from the start of loaded pedalling to the end of exercise. During recovery, the patient is told to continue with no external workload (i.e., loadless pedaling) for at least 2 minutes to prevent fainting and to accelerate lactate removal.

ECG monitoring will continue during the recovery period. Heart rate will be recorded from ECG at various intervals (i.e., 1, 2, 3, 5 minutes and as needed up to 10 minuets) during recovery.

Upon completion of the cycle exercise test and at the end of the recovery period, the following assessments need to be completed Modified Borg Scale, Bidirectional Dyspnea Index, Minute Ventilation including respiratory rate, pulse oximetry and spirometry with inspiratory loop.

At any time, a patient may discontinue the test if he/she feels symptoms that are uncomfortable and limit the volunteer's ability to continue exercising. Additionally, reasons for stopping the test

for safety reason must be clearly established and known by all personnel involved in testing. These include:

Symptoms such as:

- acute chest pain;
- sudden pallor;
- loss of coordination;
- mental confusion;
- extreme dyspnea;

and signs such as:

- clinically significant abnormalities in ECG recordings during exercise;
- fall in systolic pressure below resting value or about 20 mmHg below its highest value during exercise;
- hypertension > 200 mmHg systolic or > 100 mmHg diastolic

If the exercise has been stopped for one of these reasons, the patient should be monitored in the laboratory until signs/symptoms/ECG modifications have completely resolved. Full CPR equipment should be available in the laboratory.

4.3.7.4 Additional procedures for exercise testing

The following procedures for exercise testing should be observed to reduce exercise performance variability.

Pre-exercise diet: Patients will fast 3-4 hours following study drug administration on Study Day 4. Water will be allowed to beginning 2 hours after study drug administration and volunteers should be encouraged to drink water in order to maintain an adequate hydration state. Immediately upon completion of the fast, patients will be served lunch. Patients will not be allowed to eat again until after completion of the cycle exercise test. Fluids are to be encouraged during this time.

Previous exercise: Patients should be encouraged to stay well rested and to refrain from any strenuous, fatiguing or exhausting activities (i.e., walking up flights of stairs) on the morning of the exercise test. Very strenuous, heavy type of activities, especially activities to which the volunteer is unaccustomed, can lead to muscle soreness 24-48 hours after the activity. Patients should be encouraged to refrain from any heavy lifting, exhaustive digging in the garden, etc. for 2-3 days prior to each clinic visit, especially if the patient has not performed these activities recently.

Psychological – external motivational cues: The exercise tests performed in this study are symptom-limited, i.e., the patient will stop exercising when no longer able to tolerate the discomfort associated with the exercise. As such motivational cues provided to the patient can have profound effects on exercise performance. It is imperative that external motivational cues are controlled across patients.

Time of exercise: No visual cues regarding the time of exercise should be provided to the volunteer. The patient's watch should be removed prior to exercise, and all other timekeeping devices (i.e., study staff watches, wall clocks, stopwatch, etc.) should be kept away from the volunteer's view.

Verbal encouragement: The wording and intensity of verbal encouragement provided to the patient will be standardized. Verbal encouragement will only be provided by one member of the study team, who is blinded to the results of the lung function tests. The tone of the encouragement should be enthusiastic and supportive, but not overbearing, overly loud or coercive in nature. Examples would be: "good work", "well done", "excellent job so far", "keep up the good work". Reinforcement could also consist of "that's a good pedaling rate" or if the pedaling rate is dropping you could try a positive reminder "keep up the pedaling rate – that's great".

Comfort with equipment: Patients should be instructed to bring appropriate dress for exercise (i.e., shorts or track pants, gym shoes, T-shirt or sweat shirt) when reporting in to the study center on Study Day -1 of Period I and II. This attire should be worn for the exercise test, and study staff should ensure that the volunteer is comfortable with the positioning and the equipment prior to starting the exercise.

Familiarity with test: Before starting exercise, a member of the study team should make sure that the patient is completely familiar with the type of exercise that is to be performed; for the incremental test, patients should be told that the test will feel like he/she is cycling up a hill and that each minute the slope of the hill will increase.

Understanding "exercise for as long as you can": It is extremely important that the patient understands that there is no specific time limit to any of the exercise tests, and that the test will continue as long as the patient is able to. Stress to the patients that the study team will not stop the test unless the patient feels unable to continue due to fatigue or other symptoms, there is concern for the patient's safety, or the patient is unable to maintain the required pedaling frequency.

The cycle exercise test will be captured on the pCRF in these categories: baseline-loadless pedalling, exercise and recovery phase. Each category will include (as appropriate): work load (watts) at the end of each 2 minute interval, HR (BPM), systolic BP (mmHg), diastolic BP (mmHg), RR (BPM), V_t (Liters), and SaO₂ (%).

